5.2 Statistical Methods

Subjects will be recruited until 12 subjects complete the research imaging. For subjects that are enrolled and do not complete the research PET/MR, they will be considered a screen fail and replaced. Two radiologists, a nuclear radiologist and an abdominal radiologist, will be recruited to conduct the reader study. Both the radiologists and surgeons will utilize the Revised Endometriosis Classification System.

Sensitivity and specificity of 18F-fluoroestradiol (FES) PET/MR for evaluating endometriosis will be computed by comparing imaging against surgical findings and histopathology in order to answer Aim 1. We will compute point estimates, along with 95% confidence intervals and precision estimates that may be used to plan future studies.

We will address Aim 2 in the following fashion. After imaging, we will compare the PET results against conventional MRI, using histopathology obtained at exploratory laparotomy as the gold standard. We will do this in 2 phases, first, at the patient level, and then, as an ancillary analysis, at the endometriotic implant site level. For each phase, we will report sensitivity, specificity, and accuracy of the PET results, along with associated 95% confidence intervals. We will also report sensitivity, specificity, and accuracy, along with associated 95% confidence intervals, using conventional MRI. We will use McNemar's test, constructing the 2x2 table among all patients with a surgical diagnosis of positive to compare sensitivity for PET versus conventional MRI. Similarly, we will use McNemar's test among all patients with a surgical diagnosis of negative to compare specificity for PET versus conventional MRI. P-values <0.05 for the comparison of sensitivity and specificity will be construed as evidence that sensitivity/specificity differ between PET and conventional MRI. P-values >0.05 will be considered inconclusive.

To evaluate Aim 3, whether uptake values are associated with EHP-30 and pain rating scales, we will implement a random effects linear regression model, modeling SUV-max as a function of EHP-30 and the pain rating, while controlling for patient-level covariates (BMI, race, age). We will include physician as a random effect to account for physician-level correlation. P-values <0.05 for the EHP-30 and pain rating parameter estimates will be taken as evidence of association with uptake values. P-values >0.05 will be considered inconclusive.

As a sensitivity analysis for Aim 3, we will compute Cook's distance (D) for all observations, remove observations where $D > 1$, and recalculate the above specified model, comparing model conclusions to the original analysis.

Budgetary constraints limit sample size for this study. For Aim 2 and Aim 3, precision of estimators will be low, power levels of tests will be low, and confidence intervals will be wide. However, study results are expected to be useful in a grant proposal for a future study.

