2.2 Secondary Objectives

Aim 2: To compare PET to conventional MRI, using histopathology from laparotomy as the gold standard.

Aim 3: To evaluate the association of uptake values (SUV-max) with EHP-30 and pain rating scales, controlling for BMI, race, age, and physician.

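### The Aim 3 sensitivity analysis deletes women with Cook's D above 1, a threshold that clean data from 12 women cross about half the time, so it is a misleading robustness check

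*Combined protocol and SAP*

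**What the plan says.** Section 2.2 sets Aim 3 as the association of uptake with EHP-30 and pain, "controlling for BMI, race, age, and physician". Section 5.2 specifies the model: "modeling SUV-max as a function of EHP-30 and the pain rating, while controlling for patient-level covariates (BMI, race, age"). On the clustering it says "We will include physician as a random effect to account for physician-level correlation". The sample is fixed by "Subjects will be recruited until 12 subjects complete the research imaging".

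The decision rule is stated for the two scores: "P-values <0.05 for the EHP-30 and pain rating parameter estimates will be taken as evidence of association with uptake values", and "P-values >0.05 will be considered inconclusive".

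The sensitivity analysis at the end of section 5.2 computes Cook's distance for every observation. It will then "remove observations where $D > 1$, and recalculate the above specified model, comparing model conclusions to the original analysis". The same section concedes that for Aims 2 and 3 "precision of estimators will be low, power levels of tests will be low, and confidence intervals will be wide".

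The plan does not say how often D>1 is expected by chance, how many women may be removed, how Cook's D is to be computed in a random-effects model, or how a changed conclusion is to be read.

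**The concern.** A cut-off of 1 for Cook's D is meant to catch a rare, dominating observation. That works when each observation carries a small share of the fit. Here 12 women support at least 6 coefficients, so each woman determines on average half or more of her own fitted value, and large D values can arise with no outlier present.

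The refit then tests the two scores as if the remaining women had not been selected by how they fitted. That selection makes p-values too small. Since the rule compares conclusions, and section 5.2 defines a conclusion by P<0.05, the check can display an association that the deletion itself created. Section 5.2 expects the results to be used in a grant proposal, where such a finding could be carried forward.

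**Working it through.** **Inputs from the plan.** n = 12. Fixed effects: intercept, EHP-30, pain, BMI and age (5), plus race (1, 2 or 3 terms for two, three or four categories), so p = 6, 7 or 8. Physician is a random effect. Alpha is 0.05 for each of two coefficients. The plan gives no trigger rate or error rate for Aim 3, so there is no figure to reproduce.

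**Assumptions, not in the documents.** One SUV-max per woman; two-sided tests; null, outlier-free data; normal covariates; race mix as stated below; 2 or 3 physicians where that term is fitted.

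**Step 1: what D>1 requires.** D = e²h / (p s² (1−h)²) = (r²/p) · h/(1−h), where h is leverage and r the studentized residual. So D>1 means r² > p(1−h)/h. Mean leverage is p/n = 6/12 = 0.50 for p = 6.
- h = 0.7: r² > 6 × 0.3/0.7 = 2.57, so |r| > 1.60.
- h = 0.8: r² > 6 × 0.2/0.8 = 1.50, so |r| > 1.22.
- For contrast, n = 40: mean leverage is 6/40 = 0.15. A woman at twice that (0.30) needs r² > 6 × 0.7/0.3 = 14, so |r| > 3.74.

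With 12 women, a moderately high-leverage woman with an ordinary residual is deleted.

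**Step 2: simulation.** Generate null data, fit, delete all D>1, refit, t-test. Least-squares rows use 12,000–20,000 datasets each; random-intercept rows (REML, leave-one-out Cook's D) use 3,000.

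| Model, n = 12 | Any D>1 | False positives per score where deletion occurs, before → after | Over all datasets, before → after |
|---|---|---|---|
| p = 6, continuous covariates | 45.6% | 5.2% → 17.6% | 5.1% → 10.7% |
| p = 6, race 70/30, lognormal SUV-max | 43.3% | 5.5% → 15.8% | 5.1% → 9.5% |
| p = 7, continuous covariates | 60.8% | 5.1% → 14.8% | 5.0% → 10.9% |
| p = 7, three race categories, lognormal SUV-max | 49.9% | 5.4% → 14.7% | 5.2% → 9.9% |
| p = 8, continuous covariates | 80.1% | 5.4% → 11.8% | 5.2% → 10.3% |
| p = 8, four race categories | 54.8% | 5.1% → 14.3% | 5.0% → 10.1% |
| p = 6 + physician random, 2 physicians | 42.7% | 7.8% → 19.6% | 6.7% → 11.7% |
| p = 6 + physician random, 3 physicians | 44.0% | 9.4% → 24.5% | 8.2% → 14.8% |
| Same, between-physician variance 0.5 | 47.6% | 8.3% → 25.1% | 8.6% → 16.5% |

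Monte Carlo standard error of the 17.6%: triggered sets 0.456 × 12,000 = 5,472; √(0.176 × 0.824/5,472) = 0.5 points. For the 24.5%: 0.44 × 3,000 = 1,320; √(0.245 × 0.755/1,320) = 1.2 points.

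**Step 3: reconciling the conditional and overall rates (first row).** Untriggered sets have a rate of (0.051 − 0.456 × 0.052)/0.544 = 0.050. Overall after the rule: 0.456 × 0.176 + 0.544 × 0.050 = 0.107. The rate is about three times higher where a deletion occurs and about twice as high overall.

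**Step 4: direction of switches.** In a run of 15,000 datasets (p = 6, EHP-30/pain correlation 0.5, trigger 41%), EHP-30 moved from inconclusive to significant in 13.8% of triggered sets and the other way in 1.8%. As a share of all datasets that is 0.41 × (13.8% + 1.8%) = 6.4% for this one score. For at least one of the two scores, the verdict changes in about 10–13% of all clean datasets.

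**Step 5: dependence on n.** With p = 6 the trigger rate is 45.6% at n = 12, 5.9% at n = 20 and 0.1% at n = 40.

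**Step 6: undefined D.** A woman alone in her race category has h = 1 and e = 0, so D is 0/0. Probability of such a category:
- 70/30 mix: 12 × 0.3 × 0.7¹¹ = 0.071; the majority-category term is negligible. About 7%.
- 60/25/15 mix: 12 × 0.25 × 0.75¹¹ + 12 × 0.15 × 0.85¹¹ − 132 × 0.25 × 0.15 × 0.6¹⁰ = 0.127 + 0.301 − 0.030 = 0.398. About 40%.

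**The case against.** The strongest reply is that this is a labelled sensitivity analysis of a secondary aim in a 12-woman pilot. The P<0.05 rule belongs to the all-data model, the refit is only compared with it, and the plan already warns that Aim 3 will be imprecise. Most of this stands, and it sets the weight of the point.

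Three stronger readings are tempting and are not supported:
- *The rule triples the Aim 3 false-positive rate.* Tripling holds only where a deletion occurs and only for about 6–7 coefficients. Over all datasets the refit's rate about doubles, and with 8 coefficients the conditional increase is 2.2- to 2.8-fold.
- *The refit can turn an inconclusive Aim 3 into a positive one.* Nothing in section 5.2 lets the refit replace the all-data result.
- *The comparison will usually change the conclusion.* It does so in roughly one clean dataset in eight to ten.

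It is also fair that least squares is not the planned model. With the physician random intercept, the triggered sets start at 8–9%, so part of the excess there precedes any deletion. The increase to 20–25% is still 2.5- to 3.0-fold.

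The low-power concession does not answer the point. Low power means missed associations; the problem here is associations created by deletion.

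**Conclusion.** The point holds in a limited form. With 12 women and 6 or more coefficients, D>1 fires in about 40–60% of clean datasets (6–7 coefficients) and 55–80% with 8. Where it fires, the refit's false-positive rate per score is about 15–18% (6–7 coefficients) or 12–14% (8), against about 5% before. Over all datasets it is about 10%. Changes of verdict run mainly toward significance. The rule also has no answer for a woman who is alone in her race category.

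The all-data analysis and its error rate are unaffected. What fails is the check, because agreement or disagreement between the two fits says little about robustness. This is a point to consider, not an obstacle to the study.

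The sizes rest on assumed covariate distributions, race mixes and physician numbers, and on one SUV-max per woman. Lesion-level observations, or separate models for the two scores, would change them. With 5 coefficients, for example, the trigger rate is 33% and the refit rate 18%.

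**What to change.** In section 5.2, replace the deletion rule with text to this effect:

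> The Aim 3 conclusion rests on the model fitted to all women. To describe influence, the specified model will be refitted 12 times, leaving out one woman each time. The range of the EHP-30 and pain estimates will be reported beside the all-data estimates and 95% confidence intervals. Cook's distance will be tabulated by study code for description only. No p-value will be reported after removal of observations chosen from the data.

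Add that a woman alone in her race category has undefined Cook's D. Her leave-one-out refit is still defined: her race term drops out and, under least squares or REML, the EHP-30 and pain estimates do not change.

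Do not add a threshold that flags any woman whose removal reverses the sign or more than halves an estimate. In clean null data that flag fires for at least one score in over 90% of datasets. If a Spearman correlation is wanted, label it as a supplementary unadjusted description, since it drops the adjustment that Aim 3 requires.

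Cost: a few sentences and 12 refits, with no new data. The only loss is the significance comparison after deletion.

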5.3 Sample Size Rationale

With 12 patients, we will have 80% power at $\alpha=.05$ to detect an odds ratio of 21.91 for comparing sensitivities between PET/MRI versus conventional MRI. The detectable OR will be >10000000 for comparing specificities between PET/MRI versus conventional MRI.

Given our analysis strategy, McNemar's test, the following information was needed for the power calculation for detecting differences in sensitivity between 2 modalities: the total number of patients and the anticipated proportion of discordant pairs. We used 12 for the number of patients due to budget constraints for the pilot study. The proportion of discordant pairs is the percentage of test results that do not agree between PET/MRI and conventional MRI. We estimated this to be 55% based on published studies about MRI and the Cosmal et al. study. From this, we estimated an odds ratio of 21.91. Power calculations are made using GPower, version 3.1.9.2.

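### The detectable odds ratio of 21.91 in Section 5.3 does not follow from 12 patients and 55% discordance, and neither the number of positives nor the McNemar version is stated

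*Combined protocol and SAP*

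**What the plan says.** Section 5.3 gives the plan's only numerical power statement: with 12 patients, 80% power at alpha .05 "to detect an odds ratio of 21.91 for comparing sensitivities between PET/MRI versus conventional MRI". It names two inputs, "the total number of patients and the anticipated proportion of discordant pairs". On the first it says "We used 12 for the number of patients due to budget constraints for the pilot study"; on the second, "We estimated this to be 55% based on published studies about MRI" and on the earlier small FES study. It then concludes: "From this, we estimated an odds ratio of 21.91". For the other comparison it says: "The detectable OR will be >10000000 for comparing specificities between PET/MRI versus conventional MRI".

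Section 5.2 defines the tests. The sensitivity comparison uses McNemar's test, "constructing the 2x2 table among all patients with a surgical diagnosis of positive to compare sensitivity for PET versus conventional MRI". The specificity comparison uses "McNemar's test among all patients with a surgical diagnosis of negative to compare specificity for PET versus conventional MRI". A p-value below 0.05 is read as evidence that the modalities differ, and one above 0.05 as inconclusive. Section 5.2 ends by warning that power for Aim 2 will be low.

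**The concern.** Three things do not fit together.

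- **The figure and its inputs.** Twelve patients at 55% discordance give 6.6 expected discordant pairs, but 21.91 is the value for exactly five.
- **The analysis set.** Section 5.3 uses all 12 patients for sensitivity. Section 5.2 uses only the surgically positive women. Neither section gives an expected number of positives or negatives.
- **The test.** Neither section says whether McNemar's test is exact, mid-p, uncorrected or continuity-corrected, or whether it is one- or two-sided. With so few pairs this choice can decide the result.

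Two things are at stake. Section 5.2 says the results should support a future grant proposal, so the power figure may be carried forward with them. And because the version is open, the same Aim 2 data could be called evidence or inconclusive, depending on a choice made after the data are seen.

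**Working it through.** **Inputs.** From Section 5.3: alpha .05, power 80%, OR 21.91, 12 patients, 55% discordance. From Section 5.2: sensitivity is tested in surgical positives only. The number of positives is not given, so I take 9 to 12 as an assumed range.

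**Model.** Among discordant pairs, the probability that PET is the correct one is p = OR/(1 + OR). At OR 21.91, p = 21.91/22.91 = 0.9564.

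**Step 1: where 21.91 comes from.** With five discordant pairs, only a 5–0 split can be significant, so power is p⁵. Setting p⁵ = 0.8 gives p = 0.8^(1/5) = 0.95635 and OR = 0.95635/0.04365 = 21.911. This matches the stated figure to two decimals.

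**Step 2: the stated inputs with a fixed count.** 12 × 0.55 = 6.6. In a two-sided test, six or seven pairs must also all point one way:

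- six pairs: 0.8^(1/6)/(1 − 0.8^(1/6)) = 26.39; power at OR 21.91 is 0.9564⁶ = 76.5%
- seven pairs: 0.8^(1/7)/(1 − 0.8^(1/7)) = 30.87; power at OR 21.91 is 0.9564⁷ = 73.2%

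One-sided, seven pairs would need only 7.37 (uncorrected or mid-p), because a 6–1 split then rejects. That is not 21.91 either.

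**Step 3: the stated inputs with a random count.** Power = Σ over d of Bin(d; n, 0.55) × P(reject | d, p), where n is the number of positives. I solved for the OR at 80% power with uncorrected, corrected, mid-p and exact tests, one- and two-sided, for n = 5 to 12. None gives 21.91. The nearest are 22.3 (two-sided uncorrected, n = 12) and 22.9 (one-sided uncorrected, n = 9).

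**Step 4: power at OR 21.91 and 55% discordance.** The implied sensitivity difference is 0.55 × (21.91 − 1)/(21.91 + 1) = 0.502.

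| Positives | Two-sided uncorrected | Two-sided mid-p | Two-sided exact | One-sided uncorrected |
|---|---|---|---|---|
| 12 | 79.7% | 73.4% | 57.1% | 88.0% |
| 11 | 76.2% | 66.7% | 48.1% | 85.4% |
| 10 | 72.0% | 58.6% | 37.9% | 82.5% |
| 9 | 66.6% | 48.8% | 27.1% | 79.4% |

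The two-sided corrected test has the same power as the two-sided exact test here. Even at an infinite OR, the two-sided exact test with 12 positives reaches only 73.9%.

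**Step 5: the version and the verdict.** Two-sided p-values for a 5–0 split are 0.025 (uncorrected), 0.031 (mid-p), 0.0625 (exact) and 0.074 (corrected). Five pairs can therefore never be significant with a two-sided exact or corrected test, so 21.91 cannot have come from either.

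**Step 6: the 55%.** Section 1.2 reports nine lesions in four patients, four seen on MRI and eight on PET. The overlap must be three or four lesions, so discordance is 6/9 or 4/9. With 12 positives and OR 21.91, two-sided power at 4/9 and at 6/9 is 69% and 88% (uncorrected), 54% and 86% (mid-p), or 35% and 76% (exact). These are lesion counts, whereas the first-phase comparison in 5.2 is by patient.

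**Step 7: specificity.** With three negatives, the most extreme split (3–0) gives two-sided p = 0.083 (uncorrected), 0.125 (mid-p) or 0.25 (exact and corrected). No two-sided version can reach 0.05 with three or fewer negatives.

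**The case against.** **One ordinary reading nearly rescues the sentence.** With a two-sided uncorrected test, 12 positives and a random count, power at OR 21.91 is 79.7%, which rounds to 80%. So it would be wrong to say the 80% fails under every version. But this reading needs all 12 women to be surgically positive, which leaves nobody for the specificity test. With 11 or fewer positives, two-sided power is at most 76%. The 80% odds ratio under this reading is also 22.3, not 21.91.

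**A split of the 12 may have been used and not reported.** Nine positives give 9 × 0.55 = 4.95, or about five pairs. The remaining three negatives would explain an essentially infinite detectable odds ratio for specificity. This is plausible, but it is an inference that no section states. If it is right, 12 was not the input to the sensitivity calculation, although 5.3 says it was.

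**The stakes are low.** This stands. Aim 2 is secondary, the sample size is fixed by budget, and 5.2 already warns of low power. That warning does not contradict 5.3, which claims 80% only for a difference of about 50 points. But a general caution neither corrects a specific figure nor supplies the missing test version.

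**Conclusion.** The concern holds. Either 21.91 or its stated input of 12 patients is wrong. The figure corresponds to five fixed discordant pairs, and no version tried with 12 patients and 55% discordance returns it.

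For the two-sided test that 5.2 implies, power at the stated effect lies between 80% (uncorrected, 12 positives) and 27% (exact, 9 positives). Going from 12 to 9 positives costs 13 points with the uncorrected test. One- versus two-sided testing is worth 8 points at 12 positives and 13 points at 9. These figures assume 55% discordance, a binomial number of discordant pairs, and 9 to 12 positives; only the 55% comes from the plan.

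This should be fixed, but it does not threaten the trial. Enrolment and the Aim 1 estimates are unaffected.

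**What to change.** In Section 5.2, name the McNemar version and state that it is two-sided. To help the choice: with 8 to 12 positives, the maximum type I error over all discordance rates is 5.2–7.0% for the uncorrected test, 4.2–7.0% for mid-p and 1.6–3.9% for exact.

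In Section 5.3, replace the sentence on 80% power and OR 21.91 with text such as:

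> N = 12 is set by budget. The sensitivity comparison includes only women with a positive surgical diagnosis, whose number is not known in advance. With the two-sided [version] McNemar test at alpha .05, an assumed discordance of 55% and a sensitivity difference of about 50 points, power with 12/11/10/9 positives is [80/76/72/67% uncorrected; 73/67/59/49% mid-p; 57/48/38/27% exact].

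Keep only the row for the chosen version. Also:

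- state any split of positives and negatives that was assumed, including the number of negatives behind the specificity figure;
- label 55% as an assumption and give a range; if 4/9 to 6/9 is used, say that these are lesion counts from four patients;
- add that with three or fewer negatives no two-sided version can reach p < 0.05 for specificity.

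The cost is a rewrite of 5.3 and one phrase in 5.2. The stated power becomes less favourable. No extra patients and no change of procedure are needed.

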5.4 Interim Analysis

Interim analyses will not be conducted.

6. ADVERSE EVENTS (DRUGS- CONTRAST AGENTS)

6.1 Definitions

6.1.1 Adverse Event (AE)

An adverse event (AE) is any untoward medical occurrence (e.g., an abnormal laboratory finding, symptom, or disease temporally associated with the use of a drug) in a patient or clinical investigation subject administered a pharmaceutical product and which does not necessarily have a causal relationship with this treatment. An AE can therefore be any unfavorable and unintended sign (including an abnormal laboratory finding), symptom, or disease temporally associated with the use of a medicinal product, whether or not related to the medicinal product.

Hospitalization for elective surgery or routine clinical procedures that are not the result of an AE (e.g., surgical insertion of central line) need not be considered AEs and should not be recorded as an AE. Disease progression should not be recorded as an AE, unless it is attributable by the investigator to the study therapy.

6.1.2 Suspected Adverse Reaction (SAR)

A suspected adverse reaction (SAR) is any AE for which there is a reasonable possibility that the drug is the cause. Reasonable possibility means that there is evidence to suggest a causal relationship between the drug and the AE. A suspected adverse reaction implies a lesser degree of certainty about causality than adverse reaction, which means any adverse event caused by a drug.

Causality assessment to a study drug is a medical judgment made in consideration of the following factors: temporal relationship of the AE to study drug exposure, known mechanism of action or side effect profile of study treatment, other recent or

concomitant drug exposures, normal clinical course of the disease under investigation, and any other underlying or concurrent medical conditions. Other factors to consider in considering drug as the cause of the AE:

Single occurrence of an uncommon event known to be strongly associated with drug exposure (e.g., angioedema, hepatic injury, Stevens-Johnson Syndrome)

One or more occurrences of an event not commonly associated with drug exposure, but otherwise uncommon in the population (e.g., tendon rupture); often more than once occurrence from one or multiple studies would be needed before the sponsor-investigator could determine that there is reasonable possibility that the drug caused the event.

An aggregate analysis of specific events observed in a clinical trial that indicates the events occur more frequently in the drug treatment group than in a concurrent or historical control group

